- Unconfirmed irPD = Any irPD record after study day 1 and no record of irPD confirmed 4 weeks after, which include the situation that the PI can discontinue a patient from the study for the reason of PD without confirmation of PD after 4 weeks if patients have rapid symptomatic progression accompanied by a decline in performance status.

The assessment made by the investigator will be used for all summaries.

Best response is defined to be the best irRC response (irCR > irPR > irSD > irPD) evaluated after dosing until treatment discontinuation. Patients without post-baseline evaluations will be considered as unevaluable. Additional categories are defined for response (irCR + irPR) and disease control (irCR + irPR + irSD).

Tables will summarize the number and percentage of the best overall tumor response for each category by dose cohort, the number, percentage, and Wilson Score 95% CI will also be presented for the response categories of irCR, response, and disease control.

The percent change in tumor burden from baseline will be presented at each posttreatment tumor assessment graphically and in patient data listings. Percent change will be calculated as 100\*[(current tumor burden - baseline tumor burden)/baseline tumor burden]. The best change, i.e., the minimum of percent change from baseline for each patient will be displayed in a waterfall plot.

A by-patient listing of irRC assessment will be provided.

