#### 8.6.2.3. Tumor Markers

CA-125 and WT1 by RT-PCR will be summarized for only ovarian cancer and AML patients, respectively. Additional tumor markers may be identified and summarized as appropriate.

To evaluate the response according to CA-125, the definition of response described in Rustin, et al. [Rustin-2011] will be used. A response according to CA-125 has occurred if there is at least a 50% reduction in CA-125 levels from baseline sample. This response must be confirmed at least 28 days later by a repeat assessment that is a at least a 50% reduction or is within 10% ( $\pm$  10%) using the same assay method. Additionally, the baseline must be at least 2 times the upper limit of normal and drawn within 4 weeks prior to first dose date. Progression is defined as an increase of 2 times the nadir value at any time. If the nadir is less than the upper limit of normal then a progression will be declared at 2 times the upper limit of normal. This must be confirmed at least one week

later. Not-response/Non-PD will be assessed if neither the criteria of response or progression are achieved. A table will present the number and percentage of patients for their best response (response>Not-response/Non-PD>progression) for the CA-125 population. Additionally, the percent change from baseline may be presented over time graphically.

The descriptive statistics for the log transformed RT-PCR value will be presented for bone marrow and blood separately by each assessment and by different cohort. For any assessment, if there are multiple assessments within each category (either bone marrow or blood), choose the highest one. If the result of RT-PCR is undetectable, impute it as half of  $5.0 \times 10 \text{ copy}/\mu g$  RNA. The percent change from baseline will be presented over time graphically for WT1 by RT-PCR for the log transformed RT-PCT values.

Additionally, other markers identified upon review may be summarized and/or categorized according to standard criteria.

A by-patient listing for both CA-125, WT1 by RT-PCR, and other tumor markers identified will be provided separately.

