## 8.6.3. Exploratory Analyses

The Population for Biomarkers includes all patients in the Safety population who have the Day 29 biomarker assessment completed. All other exploratory analyses will use all patients in the Safety population of patients with the endpoint of interest measured at baseline and at least once posttreatment.

Biomarker sample collection will be conducted as indicated on the Schedules of Assessment (Table 1 and 2). Tables may summarize the statistics at the screening assessment, at each posttreatment visit, and at the end of study.

A table will summarize the Spearman rank correlation and 95% CI between the level of expression of WT1 protein and the degree of the immune response by dose cohort at each visit as measured by CTL induction. Additionally, the correlation at each visit may be presented graphically.

Scatter plots of maximum (mean, median) post-baseline values of immune response measured by CTL induction versus maximum (mean, median) post-baseline values of CA-125 will be presented. Additionally, scatter plots of maximum (mean, median) post-baseline values of immune response measured by CTL induction versus maximum (mean, median post-baseline values of WT1 by RT-PCR will be presented.

A listings of level of expression of WT1 protein will be provided.

If additional reports are provided by the biomarker vendor(s) then additional analyses may be performed and the vendor's report will be an appendix to the clinical study report.

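### The CTL-versus-marker scatter plots in SAP 8.6.3 use post-baseline levels with no baseline reference on either axis, which weakens any real link they are meant to show

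*SAP*

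**What the plan says.** SAP 8.6.3 (Exploratory Analyses) plans "Scatter plots of maximum (mean, median) post-baseline values of immune response measured by CTL induction versus maximum (mean, median) post-baseline values of CA-125". The companion display puts CTL against "maximum (mean, median post-baseline values of WT1 by RT-PCR will be presented". The marker axis is thus a per-patient summary of levels after baseline. No baseline value, change score, nadir or response category enters.

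SAP 8.6.2.3 (Tumor Markers) judges CA-125 within the patient:
- "A response according to CA-125 has occurred if there is at least a 50% reduction in CA-125 levels from baseline sample".
- For a response, "the baseline must be at least 2 times the upper limit of normal".
- "Progression is defined as an increase of 2 times the nadir value at any time", with twice the upper limit of normal (ULN) as the threshold when the nadir is below the ULN.

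SAP 8.6.3.1 (CTL Evaluation) likewise defines a CTL responder by a rise of at least 2-fold over baseline, or by any positive value when baseline is zero.

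Marker change from baseline is displayed only over time in 8.6.2.3, as an option for CA-125 and as planned for log WT1. SAP 8.6.3.2 tabulates WT1 change by cohort, and 8.6.3.1 plots CTL percent change over time. The Spearman table in 8.6.3 pairs CTL with WT1 protein expression, not with marker outcome. No planned display sets CTL against marker change.

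**The concern.** A high CTL value is favourable and a high marker value is not. What counts as antitumor effect on CA-125 is a fall from the patient's own starting point. A level after baseline combines that change with the burden at entry, and patients can differ widely in entry burden. Every CA-125 responder must also start at 2 x ULN or more, which pushes responders up a level axis, while a patient can progress at a low absolute level.

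These are the only planned displays that link the immune response to marker outcome. If entry burden dominates the vertical spread, a true relation between CTL induction and marker decline will look weaker than it is. A reader of the clinical study report could then take a weak-looking plot as absence of a link.

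**Working it through.** The plan states no sample size, correlation or precision for these plots, so there is no figure to reproduce. The check is a worked example under the SAP's own rules, then simulation under stated assumptions.

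**Worked example** (CA-125 in multiples of ULN, values assumed, draws four weeks apart).

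| | Baseline | Post-baseline | Maximum | Mean | Median | Best change | Last change |
|---|---|---|---|---|---|---|---|
| Responder | 20 | 18, 9, 8, 8 | 18 | 43/4 = 10.75 | 8.5 | 8/20 - 1 = -60% | -60% |
| Progressor | 2 | 2, 2.5, 4.5, 5 | 5 | 14/4 = 3.5 | 3.5 | 2/2 - 1 = 0% | 5/2 - 1 = +150% |

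The first patient has a confirmed fall of at least 50% from a baseline above 2 x ULN. The second has a confirmed value of at least twice a nadir of 2. The responder plots above the progressor on all three planned summaries. Change from baseline restores the order. The progressor's best change is 0%, so the best value alone does not show the rise; the last value does.

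**Model A.** Log marker is linear over 4 post-baseline draws, with slope SD 0.35 per draw, true CTL-to-slope correlation 0.7, assay noise SD 0.15 (baseline sample included) and median baseline 5 x ULN; 1,500 replicates per setting. The sizes 6, 10 and 16 follow SAP 4.1: at least 6 patients per tumor type, cohorts of 10, and 6 + 10 = 16. Entries are mean Spearman correlation of CTL with the marker maximum / with best change from baseline. Loss = 1 - (level correlation / change correlation).

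| SD of ln(baseline) | n = 6 | n = 10 | n = 16 | Loss |
|---|---|---|---|---|
| 0.5 | -0.49 / -0.57 | -0.53 / -0.61 | -0.53 / -0.62 | 13-15% |
| 1.0 | -0.37 / -0.58 | -0.38 / -0.59 | -0.40 / -0.62 | 35-36% |
| 1.5 | -0.28 / -0.57 | -0.30 / -0.61 | -0.31 / -0.62 | 50-51% |

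For example, at n = 16 and SD 1.5, 1 - 0.31/0.62 = 50%. The marker mean and median give correlations within about 0.02 of the maximum. Last change gives -0.60 to -0.64 throughout. The share of responder-progressor pairs in which the responder has the higher maximum averages about 0%, 6% and 14-16% at the three SDs.

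**Model B.** Slope per draw = 0.15 - 0.15z + N(0, 0.15), CTL = z + N(0, 0.4), 2 to 8 draws, marker noise SD 0.15 on all samples, n = 24 (an assumption, not a figure from the plan). Marker maximum against minimum log-ratio to baseline:
- SD 0.5: -0.46 / -0.54, loss 1 - 0.46/0.54 = 15%
- SD 0.8: -0.39 / -0.54, loss 28%
- SD 1.2: -0.32 / -0.55, loss 42%
- SD 1.5: -0.27 / -0.54, loss 50%

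At n = 8 and SD 1.2 the means are -0.28 and -0.51, and the SD of a single trial's Spearman is about 0.35 for the maximum and 0.30 for the log-ratio.

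The figures above use CTL as a level. With mean post-baseline CTL minus baseline CTL on the CTL axis, the correlation with the minimum log-ratio in Model B is -0.51 rather than -0.54, because noise in the baseline CTL enters.

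**The case against.** The plots are exploratory, with no test, estimate or decision attached. By-patient listings of CTL, CA-125 and WT1 are planned, so a change-based plot could be built later. With perhaps 6 to 16 ovarian patients, no version of the plot will be precise. All of this stands and limits the weight of the point. It does not remove it: a display chosen after the data are seen is less persuasive than one specified beforehand.

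A reader might infer several stronger things that the documents do not support.
- **That the maximum, as the patient's worst marker value, is the fault.** SAP 8.6.3 names maximum, mean and median together, and the mean and median perform almost identically. The missing baseline is the defect.
- **That the plan contradicts its own treatment of tumor burden,** where "the minimum of percent change from baseline for each patient will be displayed in a waterfall plot". That display serves a different endpoint and does not bind a marker scatter plot. It shows only that a best-change summary is familiar in this SAP.
- **That WT1 is plotted untransformed.** SAP 8.6.3 does not state the scale, or whether blood or marrow is used. A log scale would leave the order of patients on the maximum unchanged.

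**Conclusion.** The concern holds as a cheap improvement to an exploratory display. Without a baseline reference, the marker axis mixes entry burden with response, and a true CTL-marker link is attenuated. The direction was the same in every setting tried. The size depends on the between-patient spread of baseline markers, which the documents do not give: about 15% of the Spearman correlation at a log-baseline SD of 0.5, rising to about 50% at 1.5. It is tempting to say that the plots lose half of a real association or largely hide it. That is only the upper end of an assumed range, and inverted responder-progressor pairs are a minority throughout. At n = 8, sampling variation (SD about 0.3 or more) is larger than the average gain from the change-based axis (0.51 - 0.28 = 0.23). No primary, safety or dose-escalation conclusion is touched.

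**What to change.** In SAP 8.6.3, add as the main version:
- **Marker axis:** log(post-baseline / baseline), once for the best (lowest) and once for the last post-baseline value. Use CA-125 in ovarian patients and WT1 by RT-PCR in AML, with blood and marrow in separate plots, and apply the SAP 8.6.2.3 imputation to undetectable WT1.
- **CTL axis:** post-baseline CTL minus baseline CTL. A difference, unlike a fold change, can use the zero baselines that SAP 8.6.3.1 foresees.
- **Points:** marked by the CA-125 response category of SAP 8.6.2.3.

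Keep the level plots as a supplement, with scale and sample source stated for WT1.

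No new data are needed: SAP 8.3 and 8.6.3 already require a baseline and a posttreatment value for these analyses. The costs are a few extra figures and two statistical drawbacks. The best value becomes more extreme as draws accumulate, which is why the last value is shown beside it. The CTL difference also brings in some baseline noise (-0.51 against -0.54 in Model B).

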#### 8.6.3.1. CTL Evaluation

A patient is considered a CTL responder if s/he has:

• Two or more post-baseline visits (no need to be consecutive) with >=2-fold increase from baseline, if the baseline is not 0,

Or

 Only one post-baseline visit with >=2-fold increase from baseline when the total number of post-baseline visits is <=4, if the baseline value is not 0,

 Or

• At least one post-baseline value > 0, if a patient has baseline of 0

A table will present the number and percentage of patients for their CTL response. Additionally, geometric mean, geometric SD, the mean, standard error (se), SD, median, 25 and 75 percentile of baseline assessments and the corresponding same descriptive statistics for both mean of post-baseline assessments for each patient and maximum of post-baseline assessments for each patient will be presented by dose cohort and overall, where geometric mean is

$$\mu_{\mathbf{g}} = \sqrt[n]{A_1 A_2 \cdots A_n}.$$

and geometric SD is

$$\sigma_g = \exp \sqrt{rac{\sum_{i=1}^n (\ln rac{A_i}{\mu_g})^2}{n}}.$$

The Wilcoxon singed-rank test will be performed to see the difference between the baseline assessments and the mean of post-baseline assessments for each cohort and overall as well as the difference between the baseline assessments and the maximum of post-baseline assessments for each cohort and overall. Bar plot of mean and SE of baseline and mean of post-baseline assessments will be presented as well as baseline vs. maximum of post-baseline assessments stratified by both dose cohorts and cancer types. Similar bar plots are generated for the median and quartiles.

The percent change from baseline will be presented over time graphically. A by-patient listing will be provided.

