#### Part 1:

[figure not shown]
- Vaccine Induction Phase: once every 7 days for 4 weeks (doses 1 5)
- Consolidation Phase: once every 14 days for 6 weeks (doses 6 9)
- Maintenance Phase: once every 28 days until discontinuation (dose 10 and thereafter)

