Blood sample for CTL		X		X c		X c	X c	X c		X c		X c	X c	X c	X c
Blood sample for Anti-WT1 antibody				X c			X c			X c					X c
Blood sample for PBMC isolation				X c						X c					
Blood sample for retrospective biomarker analyses				X c,o	Xº	X c	X c			X c					X c

Table 3: Schedule of Assessments for Screening and Vaccine Induction Phase – Part 2 (Continued)

	Scree	ning						Vaccino	e Inducti	on Phase a,b,t					
				1 st dose		2 nd dose	3 rd dose	4 th dose		5 th dose		6 th dose	7 th dose	8 th dose	9 th dose
	days before 1 st dose (-1 – -14/-21)	within 7 days before 1st dose (-17)	Day -2	Day 1 (-1)	Day 3	Day 8	Day 15 (-1)	Day 22 (-1)	Day 27	Day 29 (-1)	Day 31	Day 36 (-1)	Day 43 (-1)	Day 50 (-1)	Day 57 (-1)
IHC tumor samples		$X^{p,q}$													
Tumor assessment	X r									X c,s					X c,r
Adverse events		1					1		•	•	•	•	1		-
Concomitant medications															-

Abbreviations: AML = acute myeloid leukemia, CTL = cytotoxic T lymphocyte induction activity, DTH = delayed-type hypersensitivity reactivity, ECG = electrocardiogram, ECOG = Eastern Cooperative Oncology Group, FSH = follicle-stimulating hormone, HLA = human leukocyte antigen, IHC = immunohistochemistry, irRC = immune-related response criteria, IWG = International Working Group response criteria in acute myeloid leukemia, MRI = magnetic resonance imaging, PBMC = peripheral blood mononuclear cell, PET = positron-emission tomography, RT-PCR = reverse transcriptase-polymerase chain reaction, SPECT = single-photon emission computed tomography, WT1 = Wilms' tumor gene product 1

Additional dosing windows are provided for patients who may need to recover from intercurrent medical conditions (see Section 8.3.2.1 of protocol).

Footnotes continued on the next page.

<sup>b All patients should complete an End of Study visit (see 4) within 28 days after the last dose of study drug and prior to the start of alternate antineoplastic therapy.

<sup>c Prior to study drug administration.

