# 8. STATISTICAL ANALYSIS

In this section and all after, when tables are presented by posttreatment visits, the last visit will be the visit at the end of study. When applicable, visits after the start of the maintenance phase and unscheduled visits will be included in a summary of maximum and minimum values observed for each patient's posttreatment visits, i.e., the minimum and maximum values are based on all the post treatment visits.

In general descriptive statistics for continuous variables will be summarized by the mean, standard deviation, 25th percentile, median (50th percentile), 75th percentile, minimum and maximum values. When continuous variables are displayed for less than 3 patients, only the number of observations will be presented. Categorical variables will be summarized using counts and percentages.

All raw data will be presented to the original number of decimal places. The means and medians will be presented to 1 more decimal place than the raw data. The standard deviations will be presented to 2 more decimal places than the raw data.

Baseline will generally be defined as data obtained as the last non-missing value prior to the first dose of study drug, i.e., including the pre-dose assessment on Day 1, assessments during screening and other assessments prior to the first dose of study drug.

AE tables and laboratory tables will be presented by visits and by tumor group. Tumor groups are defined as groups of overall, solid tumor, and AML patients.

Unless otherwise stated, summaries will be produced by dose cohort, which is defined as the intended and starting dose to which the patient was enrolled.

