## 8.3. Analysis Populations

There are 3 planned analysis populations.

- Safety population: includes all enrolled patients who receive at least 1 dose of study drug and will be used for the analysis of all safety and efficacy data except as noted below
- DLT population: includes all patients in the Safety population who experience a DLT within the DLT evaluation period or completed the DLT evaluation without experiencing a DLT and will be used for analysis of DLT.
- Efficacy population: include all patients in the Safety population who are evaluable for response (for each irRC, IWG, CA-125 and WT1 by RT-PCR)
  - o Population for irRC response: including all the patients in the Safety population who are not AML patients and whose lesions are measureable and have at least one posttreatment assessment. (Note that any posttreatment irRC assessment is based on the baseline assessment)
  - O Population for modified IWG response: includes all the AML patients in the Safety population who have >5% marrow blasts or >50 copy/μ g RNA of quantitative RT-PCR for WT1 transcript before the first date/time of study drug and who have at least one posttreatment assessment.
  - o Population for CA-125 tumor marker: including all ovarian cancer patients in the Safety population who have a baseline CA-125 assessment and at least one assessment posttreatment.
  - Population for WT1 by RT-PCR tumor marker: includes AML patients in the Safety population who have a baseline assessment and at least one assessment posttreatment.
- Population for CTL: including all patients in the Safety population who has a baseline assessment of percentages of WT1-positive cells among CD8-positive cells and at least one post-baseline assessment

Additional populations for analyses of other tumor markers identified may be defined in a similar manner.

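### The CTL responder rule sets different bars by number of visits and by zero baseline, so responder percentages depend on follow-up as well as dose

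*SAP*

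**What the plan says.** SAP 8.6.3.1 gives three routes to CTL response.

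- Non-zero baseline, general rule: "Two or more post-baseline visits (no need to be consecutive) with >=2-fold increase from baseline, if the baseline is not 0".
- Non-zero baseline, few visits: "Only one post-baseline visit with >=2-fold increase from baseline when the total number of post-baseline visits is <=4".
- Zero baseline: "At least one post-baseline value > 0, if a patient has baseline of 0". No fold size or second visit is required.

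The rule sets no visit window and no cap on visits, and the SAP gives no detection limit or variability for this assay. SAP 8.3 admits a patient to the CTL population who "has a baseline assessment of percentages of WT1-positive cells among CD8-positive cells and at least one post-baseline assessment", so one post-baseline value is enough to enter. For baseline, SAP 8 states: "Baseline will generally be defined as data obtained as the last non-missing value prior to the first dose of study drug". One pre-dose value is thus the denominator of all of a patient's fold changes.

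The row "Blood sample for CTL" in Tables 1 to 4 of SAP 6.1 fixes how many chances a patient has. In Part 1 the phases are "Vaccine Induction Phase: once every 7 days for 4 weeks" and "Consolidation Phase: once every 14 days for 6 weeks", with sampling on each dosing day. Part 2 has longer induction and consolidation phases. SAP 8 reports by starting dose cohort, and 18 and 27 mg occur only in Part 2.

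**The concern.** A responder definition should mean the same thing for every patient in the table. Here the bar moves with two features unrelated to drug effect.

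The first is the number of visits. A Part 1 patient with one 2-fold rise among Days 8, 15, 22 and 29 is a responder on four samples. If the patient then gives one more sample, for example at End of Study, and it is not raised, there are five visits with one rise and the patient becomes a non-responder. This needs no assumption about noise. Beyond five visits, each further sample is another chance to collect the second rise.

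The second is a zero baseline, where one non-zero reading at any visit, however small, is a response.

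Dose and Part are fully confounded. A reader who sets the 18 and 27 mg responder percentages beside those for 0.3 to 9 mg is comparing dose and number of chances together.

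**Working it through.** **Plan's own figure.** None. The documents state no false-response rate, assay CV or error rate for CTL response, so the sizes below rest on assumed noise.

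**Scheduled post-baseline CTL samples** (SAP 6.1, Tables 1 to 4, without the End of Study sample, which adds one in both Parts):

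- Part 1: Days 8, 15, 22, 29, 43, 57, 71, 85 = 8, then every 28 days (113, 141, ...).
- Part 2: Days 8, 15, 22, 29, 36, 43, 50, 57 = 8, then 71, 85, 99, 113, 127, 141 = 6, total 14. The Table 4 row is broken in the text and is read here as every dosing day.

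| Follow-up to | Part 1 | Part 2 |
|---|---|---|
| Day 29 | 4 | 4 |
| Day 36 | 4 | 5 |
| Day 85 | 8 | 10 |
| Day 141 | 10 | 14 |

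**Non-zero baseline, no true effect.** Assume independent lognormal within-patient noise with log SD s and one shared noisy baseline z0. Given z0, each visit shows a 2-fold rise with probability p(z0) = 1 − Φ((ln 2 + s·z0)/s). The null responder rate is the average over z0 of P(Binomial(K, p(z0)) ≥ r), with r = 1 for K ≤ 4 and r = 2 for K ≥ 5. Results by numerical integration:

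| Log SD (CV) | K = 4 | K = 5 | K = 8 | K = 10 | K = 14 |
|---|---|---|---|---|---|
| 0.198 (20%) | 2.3% | 0.5% | 0.9% | 1.2% | 1.8% |
| 0.3 (31%) | 14.7% | 5.7% | 9.5% | 11.8% | 15.5% |
| 0.5 (53%) | 38.2% | 21.8% | 31.5% | 36.3% | 43.4% |
| 0.7 (80%) | 51.0% | 33.2% | 45.0% | 50.3% | 57.8% |

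The rate rises to four visits, drops at five, then rises again.

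**Parts at matched follow-up, log SD 0.3/0.5/0.7.**

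- Day 29: 4 vs 4 visits, no difference.
- Day 36: 4 vs 5 visits, 14.7/38.2/51.0% in Part 1 vs 5.7/21.8/33.2% in Part 2. Part 1 is higher.
- Day 141: 10 vs 14 visits, 11.8/36.3/50.3% vs 15.5/43.4/57.8%. The gap is 3.7/7.1/7.5 points, with Part 2 higher.

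**Zero baseline, no true effect.** If a fraction q of null samples reads above 0 (assumed), the rate is 1 − (1 − q)^K. For q = 2/5/10%: K = 4 gives 7.8/18.5/34.4%, K = 10 gives 18.3/40.1/65.1%, and K = 14 gives 24.6/51.2/77.1%.

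**Fixed window, Days 8 to 29, two visits required.** With all four samples and a non-zero baseline, the null rate is 4.2/17.5/27.6% at log SD 0.3/0.5/0.7, the same in both Parts. For a zero baseline with two positive values required, it is 1.4% at q = 5% and 5.2% at q = 10%.

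**The case against.** Several points on the other side stand.

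- **Status.** The secondary variable in SAP 6.3 is the CTL measurement at each assessment time. The responder classification sits under exploratory analyses, is a count and percentage, and has no planned test between cohorts or Parts. SAP 8.6.3.1 also gives summaries of each patient's post-baseline mean, a signed-rank test on that mean, percent change over time and a listing. No stated error rate is broken.
- **Inputs.** Neither the assay noise, the frequency of zero baselines nor the rate of positive readings among them is documented. At a CV of 20% the non-zero-baseline rates are negligible.
- **Cohorts within a Part.** These share one schedule. Bias between them needs different follow-up or a different share of zero baselines, and the documents show neither.

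A reader might infer that Part 2 patients have 14 chances against 8 in Part 1. That compares Day 141 with Day 85. Part 1 patients go on giving samples in maintenance, so the matched count is 10 against 14. A reader might also infer that a higher responder rate at 18 and 27 mg could come wholly from denser sampling. For non-zero baselines this is not supported. With approximately 10 patients per Part 2 dose, one patient is 10 points, and the matched gap of about 4 to 8 points is less than one patient per cohort. The direction can also reverse when patients leave early.

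None of this removes the drop between four and five visits or the unconfirmed zero-baseline route. Both are in the rule as written.

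**Conclusion.** The concern holds in a limited form. The rule applies unequal bars, so the chance of a false response varies with the number of samples and with a zero baseline, and responder percentages across Parts mix dose with number of chances after Day 29. The largest step for non-zero baselines is between four and five visits: 15/38/51% against 6/22/33% at log SD 0.3/0.5/0.7. The matched Part 1 to Part 2 gap at Day 141 is about 4 to 8 points, and it is nil through Day 29. For zero baselines the rates can be large, but only under an assumed positivity rate.

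All sizes assume no true effect, independent visits and noise levels that the documents do not give. They do not show that the cohorts or Parts cannot be compared at all. They show that a comparison needs a common window and a single bar. The change should be made before analysis, in proportion to a descriptive exploratory table.

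**What to change.** In SAP 8.6.3.1:

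1. Keep the all-visit responder table as a description.
2. Add a fixed-window responder rate from Days 8, 15, 22 and 29, which are sampled in both Parts, and name it as the version for any comparison across cohorts or Parts. Require a 2-fold rise at two of these visits for every patient with a non-zero baseline, whatever the number of visits.
3. Show zero-baseline patients in a separate row, requiring values above 0 at two visits in the same window.
4. Report, by cohort, the number of patients with fewer than two evaluable samples in the window.

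The cost is a paragraph of SAP text and one more derivation and table. Later and single-visit rises do not count in this version, so its rate will be lower, possibly substantially: under the null at log SD 0.5, a patient with four visits falls from 38% to 17.5%. Responses that first appear during the extended Part 2 phases are seen only in the all-visit table. Some dependence on attendance remains inside the window (at log SD 0.5, 6.5% with two samples against 17.5% with four), which is why item 4 is needed.
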